#### *Secondary study endpoint*

- Geometric mean titers of serum antibodies to antigens according to assessment at Day 21 after immunization (Visit 7)

The comparison will be performed by calculation of two-sided 95 % confidence interval using ANCOVA covariance analysis upon log base 10 transformation. ANCOVA model will include the vaccine as a fixed factor and the baseline antibody titer log as a covariate. The clinical center, sex, and age will also be considered as potential factors of the model. The difference between mean values in the compared groups (comparator test) will be evaluated together with the respective 95 % confidence interval. Point estimate of mean differences and the respective confidence interval will be subjected to inverse transformation.

---

Strictly confidential. Proprietary Information.  
[name]

If the upper limit of the calculated 95 % confidence interval for GMAT1/GMAT2 ratios (GMAT1 and GMAT2 — geometric mean titers of serum antibodies to antigens for the reference vaccine and the test vaccine respectively) does not exceed the limit of 1.5, the test vaccine will be considered as not inferior to the comparator for the endpoint, the share of subjects achieving seroconversion according to the evaluation at Day 21 after immunization. In case of proven non-inferiority of the test vaccine versus the reference vaccines for Yamagata and Victoria lineages antigens the same two-sided 95 % confidence interval shall be used for testing of the hypothesis of predominant efficacy of the test vaccine for this endpoint. This conclusion will be made if the upper limit of the calculated 95 % confidence interval does not exceed 1.

- Coefficient of increase of mean geometric antibody titer (antigens H1N1, H3N2, Yamagata and Victoria lineages), based on evaluation at Day 21 after immunization versus baseline (Visit 7)

GMAT ratio before and after immunization will be evaluated with the respective two-sided 95 % confidence interval based on log transformation ( $\log_{10}$ ), point estimate of the difference and the confidence interval, and inverse transformation of the obtained values. The lower limit of the obtained confidence interval for GMAT ratio shall be positioned to the right of the defined limit of 2.5.

- Seroprotection: share of subjects achieving protective antibody titer (1:40 and more) to antigens H1N1, H3N2, Yamagata and Victoria lineage, based on assessment at Day 21 after immunization (Visit 7).

The shares of subjects achieving seroprotection will be presented with two-sided exact 95 % confidence intervals. Intergroup comparisons will be performed based on the exact Fisher test, as well as based on logistic regression with the vaccine as a fixed factor and the baseline antibody titer log as a covariate. The clinical center, sex, and age will also be considered as potential factors of the model.

- Incidence of influenza and ARI based on assessment 180±5 days after immunization (Visit 11).

Incidence of the disease will be presented with the respective two-sided 95 % confidence interval for therapeutic groups. The parameter will be analyzed using the Kaplan-Meier survival method (time to the first episode of the disease).

- Evaluation of severity and duration of reported cases of influenza and ARI, symptoms and complications will be presented descriptively for therapeutic groups.

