Immunogenicity and efficacy endpoints	
Primary:
 

• The share of subjects achieving seroconversion (the number of volunteers with antibody titer [of at least 1:40] increased more than 4-fold versus baseline [assessed by HAIR]) for antigens: influenza virus type A — H1N1, influenza virus type A — H3N2, influenza virus type B — Yamagata and Victoria lineage, based on assessment at Day 21 after immunization (Visit 7).

 
Secondary:
 

• Coefficient of increase of mean geometric antibody titer (antigens H1N1, H3N2, Yamagata and Victoria lineages) based on assessment data after 21 days following vaccination (visit 7).

• Geometric mean of serum antibodies to antigens: influenza virus type A — H1N1, influenza virus type A — H3N2, influenza virus type B — Yamagata and Victoria lineage, based on assessment at Day 21 after immunization (Visit 7).

• Seroprotection: share of subjects achieving protective antibody titer (1:40 and more) to antigens H1N1, H3N2, Yamagata and Victoria lineage, based on assessment at Day 21 after immunization (Visit 7).

• Incidence of influenza and ARI based on assessment 180±5 days after immunization (Visit 11).

• Severity and duration of reported cases of influenza and ARI, complications.

Safety and reactogenicity parameters	

• Quantitative assessment and nature (severity and duration) of local and systemic reactions to vaccine administration.

• AEs and SAEs associated with the study vaccines.

• Immediate type AEs, emerging within one hour after immunization.

• Incidence and nature of intercurrent disorders

• Vital function assessment results.

• Results of physical examination.

• Neurological examination results.

• Results of blood hematology and biochemistry tests.

Strictly confidential. Proprietary Information.  
[name]

	

• Urinalysis results.

• Immunological parameters evaluation results: serum immunoglobulin content (ELISA: IgE).

Statistical analysis	See Section 8 of the protocol.

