#### **Influenza and ARI incidence recording:**

Influenza and ARI incidence recording is performed during 6 months after immunization by means of follow-up and telephone calls to the study subjects.

A case of influenza and ARI is considered as a case of flu-like symptoms (according to: ECDC TECHNICAL DOCUMENT Protocol for case-control studies to measure pandemic and seasonal influenza vaccine effectiveness in the European Union and European Economic Area Member States / European center for Disease Prevention and Control, 2009):

*if a subject seeks physician's advice regarding unexpected occurrence of*

*- at least one of four systemic symptoms: 1) chills or fever, 2) distress, 3) headache, 4) myalgia and*

*- - of at least one of three respiratory symptoms: 1) cough, 2) sore throat, 3) respiratory distress.*

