#### **Evaluation of severity and duration of reported cases of influenza and ARI, complications:**

When recording a case of influenza or ARI, a study doctor will perform an evaluation of its duration, making additional telephone calls, where necessary, and determine its severity. In this study, a case with at least one of the complications listed below will be considered severe:

- the necessity of hospitalization,
- influenza-associated pneumonia,
- influenza-associated cardiovascular disorder,
- death.

---

Strictly confidential. Proprietary Information.  
[name]

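### Illness duration is summarised only among volunteers who became influenza/ARI cases, and the denominator for severity is not stated, so these tables do not compare the randomised vaccine groups

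*Combined protocol and SAP*

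**What the plan says.** The Synopsis (immunogenicity and efficacy endpoints) and Section 3.1 list as a secondary efficacy endpoint "Severity and duration of reported cases of influenza and ARI, complications". Section 8.1, under the secondary endpoints, gives the whole analysis: "Evaluation of severity and duration of reported cases of influenza and ARI, symptoms and complications will be presented descriptively for therapeutic groups". No test, model or decision rule is attached. Section 8.1 defines the therapeutic groups as A, B, C and pooled B+C.

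Section 6.2 fixes how the data arise:

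- A case is medically attended: it counts "if a subject seeks physician's advice regarding unexpected occurrence of" at least one systemic and at least one respiratory symptom.
- Duration is assessed only after that point: "When recording a case of influenza or ARI, a study doctor will perform an evaluation of its duration".
- Severity is binary: "a case with at least one of the complications listed below will be considered severe". The list is hospitalisation, influenza-associated pneumonia, influenza-associated cardiovascular disorder and death.
- The observation window is stated: "Influenza and ARI incidence recording is performed during 6 months after immunization".

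Section 8.1 also says that efficacy is evaluated on available data with no imputation. No rule gives a volunteer without a case a duration of zero. Categorical results are to be shown as counts and percentages, with no denominator named for this endpoint.

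Just before the severity and duration item, Section 8.1 plans two further outputs on illness: "Incidence of the disease will be presented with the respective two-sided 95 % confidence interval for therapeutic groups", and "The parameter will be analyzed using the Kaplan-Meier survival method (time to the first episode of the disease").

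**The concern.** Randomisation makes groups A, B and C comparable as whole groups. It does not make the cases within them comparable, because becoming a case happens after vaccination and may be influenced by it. Having to seek a physician's advice is a second selection step. A difference in mean duration per case, or in the severe share of cases, therefore mixes two things: a change in how ill people become and a change in which people become ill.

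A difference in incidence is part of the product's rationale. B and C each lack one B-lineage antigen, and Sections 1.1 and 1.3 expect broader B coverage to protect better. If that expectation is right, the sets of cases will differ between groups. A vaccine that mainly removes short, mild illness would then leave a smaller set of cases with a longer average duration.

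What is at stake is how one descriptive secondary table is read, in a study whose stated objective includes efficacy against Grippol Plus. The primary endpoint and the sample size are not involved.

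**Working it through.** **Figures in the plan.** The documents state no expected incidence, duration or severe share for influenza/ARI, so there is no plan figure to reproduce for this endpoint. The only inputs taken from the plan are the group sizes in Section 8.2: 204 per group, hence 204 in A and 2 × 204 = 408 in pooled B+C. All illness rates below are assumptions.

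**Check 1: can the two summaries move in opposite directions?** Assume that 20 % of the comparator group become cases, half lasting 4 days and half 10 days. Assume the test vaccine prevents half of the short cases and none of the long ones.

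- Comparator, mean per case: (0.10 × 4 + 0.10 × 10) / 0.20 = 7.0 days. Per volunteer: 0.40 + 1.00 = 1.40 days.
- Test, mean per case: (0.05 × 4 + 0.10 × 10) / 0.15 = 8.0 days. Per volunteer: 0.20 + 1.00 = 1.20 days.

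Duration per case is 1 day worse, while burden per volunteer is 0.20 / 1.40 = 14 % lower.

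**Check 2: milder assumptions, including severity.** Assume 10 % incidence in B+C, 10 % of cases severe, 5 days for a mild case and 12 for a severe one. Assume A has 30 % fewer mild cases and the same severe risk. Per 100 vaccinated, B+C has 9 mild and 1 severe case, and A has 9 × 0.7 = 6.3 mild and 1 severe.

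| Summary | B+C | A |
|---|---|---|
| Cases per 100 vaccinated | 10 | 7.3 |
| Severe share of cases | 1/10 = 10.0 % | 1/7.3 = 13.7 % |
| Mean days per case | (9×5 + 12)/10 = 5.70 | (6.3×5 + 12)/7.3 = 5.96 |
| Severe cases per 100 vaccinated | 1.0 | 1.0 |
| Illness days per 100 vaccinated | 57.0 | 43.5 |

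The case-only rows look worse for A. The whole-group rows show equal severe risk and less illness.

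**Range.** Let s be the severe share of cases in B+C and f the fraction of mild cases prevented. The severe share in A is then 1 / [s + (1 − f)(1 − s)] times that in B+C.

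- For s from 5 % to 20 % and f from 20 % to 50 %, the factor runs from 1 / (0.20 + 0.80 × 0.80) = 1.2 to 1 / (0.05 + 0.50 × 0.95) = 1.9.
- With the same 5- and 12-day durations, the excess in mean duration in A runs from 0.08 to 0.93 days.
- With f = 0 incidence is equal, the factor is 1 and the distortion is zero.

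**Precision.** Under Check 1, A would have 204 × 0.15 = about 31 cases and B+C 408 × 0.20 = about 82. The SDs of duration are 6 × √(1/3 × 2/3) = 2.8 and 6 × √(1/2 × 1/2) = 3.0 days. The standard error of the difference is √(2.8²/31 + 3.0²/82) = 0.60 days, so the 1-day difference has a 95 % interval of about −0.2 to 2.2. Under Check 2, A has 204 × 0.073 = about 15 cases, of which 204 × 0.01 = about 2 are severe. Any such table will be imprecise.

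**The case against.** The strongest reply is that the plan treats this endpoint as description and gives the reader the context. That is largely right:

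- **Incidence is reported beside it.** Both the incidence with its confidence interval and the Kaplan-Meier analysis use all volunteers. A reader might infer that the severity and duration table is the trial's only evidence on illness burden. Section 8.1 shows that it is not.
- **Severity is partly covered elsewhere.** The safety analysis in Section 8.1 tabulates participants with adverse events by maximum severity among everyone who received a dose, and adverse events are recorded through the Day 180 call. Hospitalisation and death are also serious adverse event criteria (Section 7.3.2). However, the adverse event scale in Section 7.3.1.1 differs from the severe-case definition in Section 6.2, so that share is not produced.
- **No inference is planned.** A reader might infer that the plan would lead to a finding that Grippol Quadri causes longer or more severe illness. No test or conclusion is attached, so the documents do not support that.
- **The severity denominator is open.** It is tempting to say that severity is expressly computed among cases. The endpoint is worded per case, but the percentage base is unstated and could be either.
- **Burden can be approximated.** Incidence times mean duration recovers it in Check 1 (0.20 × 7.0 = 1.40; 0.15 × 8.0 = 1.20). This holds only with at most one case per volunteer. The plan does not say whether duration is counted per episode or per volunteer, while Kaplan-Meier uses first episodes only. The confidence interval cannot be rebuilt this way.
- **The effect may be small.** All groups receive active vaccine, and the case definition is symptom-based, which would dilute a lineage-specific effect.

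What survives is that duration has no whole-group summary, and that severe cases by the Section 6.2 definition have no stated denominator.

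**Conclusion.** The point holds in a limited form. Duration by vaccine group describes a subset formed after randomisation, as does severity if cases are the denominator. Neither then compares the randomised groups, and either can point the opposite way to total burden when incidence differs. Under the assumed inputs in Check 2, the shift is 0.26 days in mean duration (5.96 − 5.70) and 3.7 percentage points in severe share (13.7 − 10.0), with severe risk per volunteer unchanged and 13.5 fewer illness days per 100 vaccinated (57.0 − 43.5).

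These sizes rest wholly on assumed incidence, severity mix and durations, and on the vaccine preventing mild cases only. They show what is possible and do not predict what this trial will find. With equal incidence this distortion is absent. The matter is minor: it concerns the interpretation of one descriptive secondary endpoint.

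**What to change.** Keep the case-only tables, state their denominator, and label them as description that does not compare vaccines. Add one table for A, B, C and pooled B+C, with 95 % confidence intervals, showing:

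1. Illness days per vaccinated volunteer, summed over all episodes, with 0 for volunteers followed with no case. Incomplete follow-up should be accounted for, for example by expressing days per unit of follow-up time.
2. The share of all vaccinated volunteers with a severe or complicated case by the Section 6.2 definition.

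The cost is one extra descriptive table with wide intervals. No new data, visits or volunteers are needed, and the primary endpoint and sample size do not change.

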#### *Safety analysis*

The safety analysis will be conducted by descriptive methods in the safety population. Adverse events will be coded using MedDRA. The number (percentage) of participants with AEs and the number of AEs will be presented in tables by system organ class and preferred term, as well as by the study therapy and severity.

---

Strictly confidential. Proprietary Information.  
[name]

With that, within a system organ class and preferred term, each subject will be considered once with regard to study therapy and maximum severity. The number (percentage) of volunteers with local and general reactions to vaccination will be presented taking into account severity and duration.

Laboratory findings and their changes after vaccination compared to the baseline and “shift tables” relative to normal values will be tabulated by therapeutic groups and by assessment points.

The results of the assessment of vital functions will be tabulated by therapeutic groups for each assessment point together with changes from the last available measurement prior to vaccination.

The results of physical examination will be presented descriptively by therapeutic groups and by assessment points.

Immunological parameters evaluation results: serum immunoglobulin content (ELISA: IgE) and their changes after vaccination compared to baseline values will be tabulated by therapeutic groups.

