Only the subjects without any intercurrent conditions within the first five days after immunization were included in the system reactions analysis: in total 29 of the 30 subjects from the group Grippol® Quadri, 28 of 30 subjects from the group Grippol® Plus, and 29 subjects from the Placebo group. During the evaluation of the reactogenicity, the general reactions were detected in the group Grippol® Quadri in 20.7 % of the subjects, in the group Grippol® Plus in 3.6 % of the subjects, and in the Placebo group in 10.3 % of the subjects. Among the general reactions recorded during the study, there were the following: rise in body temperature above 37 °C, malaise, headache, nausea, myalgia / arthralgia. The most common general reaction in the group Grippol® Quadri was the development of headache — in 13.8 % of the subjects, whereas in the group of Grippol® Plus and in the Placebo group headache was observed only in 3.6 % and 3.4 % of the subjects respectively. The rise in body temperature above 37 °C was recorded in 6.9 % of subjects in the group Grippol® Quadri (within subfebrile with a maximum registered value of 37.2 °C), and also in 6.9 % of subjects in the Placebo group (within subfebrile with a maximum registered value of 37.5 °C). All the occurred systemic reactions were regarded as mild. During the comparative evaluation, there was no evidence of the statistically significant difference between the proportion of mild, moderate, and severe local reactions in the Grippol® Quadri group, Grippol® Plus group, and Placebo group ( $p = 0.102$  and  $p = 0.470$  respectively).

Strictly confidential. Proprietary Information.  
[name]

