## 2. OBJECTIVES AND PURPOSES OF THE STUDY

The objective of this study was assessment of safety, reactogenicity, immunogenicity, and efficacy of quadrivalent inactivated subunit influenza vaccine Grippol® Quadri (NPO Petrovax Pharm, LLC, Russia) versus trivalent inactivated polymer-subunit vaccine Grippol® Plus (NPO Petrovax Pharm, LLC, Russia) in subjects from 18 to 60 years old.

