### Study goals:

- Study and comparative assessment of immunogenicity of quadrivalent inactivated subunit influenza vaccine Grippol® Quadri versus trivalent inactivated polymer-subunit vaccine Grippol® Plus in subjects from 18 to 60 years old.
- Assessment of safety and reactogenicity of the quadrivalent inactivated subunit influenza vaccine Grippol® Quadri compared to the influenza vaccine trivalent inactivated polymer subunit vaccine Grippol® Plus in volunteers ages 18–60 years old.

Strictly confidential. Proprietary Information.  
[name]

- Study and comparative assessment of immunogenicity of quadrivalent inactivated subunit influenza vaccine Grippol® Quadri versus trivalent inactivated polymer-subunit vaccine Grippol® Plus in subjects from 18 to 60 years old.

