***Systemic reactions:***

1. Increase of body temperature over 37 °C
2. Malaise
3. Headache
4. Sleep disturbance
5. Appetite disturbance
6. Nausea
7. Vomiting
8. Abdominal pains
9. Stuffy nose

---

Strictly confidential. Proprietary Information.  
[name]

10. Cough
11. Pharynx hyperaemic
12. Increased sweating
13. Tremor
14. Myalgia, arthralgia.

The nature and duration of immunization reactions in vaccinated subjects is compared upon interpretation of all study materials. An analysis of this data will make it possible to formulate a conclusion and resolve the issue of tolerability of study vaccines.

The course of the post-immunization period is assessed as smooth or complicated. Complicated course of the post-immunization period is considered as integration of intercurrent diseases after immunization. The absence of intercurrent diseases is considered as smooth post-immunization period. Fever responses were classified by temperature increase as follows: mild (low-grade fever up to 37.5 °C), moderate (temperature rise from 37.6 °C to 38.5 °C), and severe (temperature rise above 38.6 °C).

Local immunization reactions are classified as mild, moderate, and severe. Erythema without infiltration up to 50.0 mm in diameter at the injection site or infiltration up to 25.0 mm in diameter is estimated as a mild local reaction; erythema with a diameter more than 50.0 mm or an infiltrate with a diameter 26.0 to 50.0 mm was estimated as a moderate local reaction; infiltration more than 50.0 mm in diameter was estimated as a severe local reaction (Methodological Guidelines MU 3.3.2.1758-03 "Methods for determination of quality indicators of immunobiological products for prevention and diagnostics of influenza"). When the reaction is free of redness and/or infiltration, the reaction severity is accepted as indeterminate.

Local reactions will be assessed in all subjects, since local reactions were directly related to the administration of the vaccine.

Occurrence of general symptoms on the first 3 days after (and even on the day of immunization) may be associated with immunization (systemic reactions). However, it does not rule out their causal relationship with diseases, accidentally occurring within the first days of post-immunization period.

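### Safety and reactogenicity are to be compared with Grippol Plus, but Section 8.1 plans no between-group difference or interval for reactions, adverse events or influenza/ARI

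*Combined protocol and SAP*

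**What the plan says.** Aims. Section 2 opens with a general objective that covers four domains, all relative to Grippol Plus: "The objective of this study was assessment of safety, reactogenicity, immunogenicity, and efficacy of quadrivalent inactivated subunit influenza vaccine Grippol® Quadri". One of the goals listed under it is explicitly comparative on safety: "Assessment of safety and reactogenicity of the quadrivalent inactivated subunit influenza vaccine Grippol® Quadri compared to the influenza vaccine trivalent". The first and third goals carry the same text, on immunogenicity: "Study and comparative assessment of immunogenicity of quadrivalent inactivated subunit influenza vaccine Grippol® Quadri". Clinical efficacy therefore appears in the objective and, as influenza/ARI incidence, among the secondary endpoints of Section 3.1. It is not in the list of goals.

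Reactions. Section 7.2 says: "The nature and duration of immunization reactions in vaccinated subjects is compared upon interpretation of all study materials". It adds that this will support a conclusion on tolerability, and it names no method. It also restricts the assessment of general reactions to volunteers without intercurrent disease (a smooth course).

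Analysis. Under Safety analysis, Section 8.1 says: "The safety analysis will be conducted by descriptive methods in the safety population". For reactions: "The number (percentage) of volunteers with local and general reactions to vaccination will be presented taking into account severity and duration". For influenza/ARI it gives incidence per group with a two-sided 95 % interval, and then: "The parameter will be analyzed using the Kaplan-Meier survival method (time to the first episode of the disease". The comparisons of Group A with the other groups under Efficacy analysis are defined antigen by antigen. The general paragraph of Section 8.1 offers 95 % intervals around point estimates where applicable, and it lists pooled B and C as a reporting group.

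Phase I (Section 1.2): "general reactions were detected in the group Grippol® Quadri in 20.7 % of the subjects", against 3.6 % with Grippol Plus and 10.3 % with placebo.

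**The concern.** The plan sets a comparative question and then specifies output that describes each group separately. Where the authors want a contrast they say so: GMAT has an interval for the ratio between groups, and seroprotection has Fisher's test and logistic regression. Reactions, adverse events and influenza/ARI have nothing of this kind.

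Two things are at stake. First, comparing separate group intervals by eye is a poor substitute for an interval on the difference, because separate intervals can overlap when the interval for the difference excludes zero. Second, if no contrast is fixed in advance, the choice of which groups to compare, on which denominator and with which measure, is left until after the data are seen. For influenza/ARI, a reader shown separate curves is not told how large a difference the data leave open.

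**Working it through.** **1. The plan's own figures reproduce.**
- Sample size (Section 8.2): n = (1.96 + 0.842)² / (0.15 - 0.01)² × (0.60×0.40 + 0.59×0.41) = 192.98, so 193 per group. Then 193/0.95 = 203.2, so 204. Pooled B and C is 2 × 204 = 408.
- Phase I systemic reactions (Section 1.2): 20.7 % of 29 is 6 and 3.6 % of 28 is 1. With placebo at 10.3 % of 29, the count is 3. Two-sided Fisher tests give p = 0.102 for 6/29 v 1/28 and p = 0.470 for 6/29 v 3/29. Both match the printed values.

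**2. What Phase I shows.** The difference is 6/29 - 1/28 = 0.207 - 0.036 = 0.171. The Wilson limits are 0.098 to 0.384 for Quadri and 0.006 to 0.177 for Plus. Newcombe limits:
- lower: 0.171 - √[(0.207 - 0.098)² + (0.177 - 0.036)²] = -0.007
- upper: 0.171 + √[(0.384 - 0.207)² + (0.036 - 0.006)²] = +0.351

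So the difference is 17.1 points (95 % CI -0.7 to +35.1), on seven events.

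**3. What this trial could show.** The documents give no expected reaction or ARI rates for this trial, so equal rates of 5 to 20 % are assumed. Half-width = 1.96 × √[p(1 - p)(1/n₁ + 1/n₂)], in percentage points:

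| Assumed rate | 204 v 408 | 204 v 204 | 193 v 386 (after 5 % dropout) |
|---|---|---|---|
| 5 % | 3.7 | 4.2 | 3.8 |
| 10 % | 5.0 | 5.8 | 5.2 |
| 20 % | 6.7 | 7.8 | 6.9 |

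If the Phase I rates recurred at 204 v 408, the half-width would be 1.96 × √(0.207×0.793/204 + 0.036×0.964/408) = 5.8 points, against about 18 in Phase I.

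**4. Why separate intervals are not enough.** Assume 10 % v 5 % at 204 v 408.
- Separate intervals: 10 ± 4.1 (5.9 to 14.1) and 5 ± 2.1 (2.9 to 7.1). They overlap.
- Difference: half-width 1.96 × √(0.09/204 + 0.0475/408) = 4.6, so 5.0 points (0.4 to 9.6), which excludes zero.
- Against one trivalent group the half-width is 5.1, and the interval includes zero.

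**5. Influenza/ARI is estimation only.** At an assumed 10 % incidence there would be 0.10 × 612 = 61.2 first episodes. The hazard ratio detectable with 80 % power would be exp[-2.802/√(61.2 × 1/3 × 2/3)] = 0.47. The trial is not sized to test this endpoint.

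**The case against.** Descriptive safety reporting is a defensible choice in a trial sized for seroconversion with formal hypotheses by antigen. The counts will be tabulated by group, so anyone can compute a risk difference. If the Phase I rates recurred, the separate intervals would be 15.1 to 26.3 % and 1.8 to 5.4 %, and the contrast would be obvious without further analysis. The 10 % v 5 % example is an assumption, and it excludes zero only narrowly and only with pooling. Influenza/ARI is defined by symptoms in people who seek medical advice, with no laboratory confirmation required, so its difference says little about protection against influenza.

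Much of this stands. It argues against adding tests, and it limits what the ARI contrast can mean. It does not answer the mismatch between a comparative goal and a plan with no contrast. That a reader can compute the difference later is no substitute for fixing the contrast, measure and denominator beforehand.

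Four stronger readings may tempt a reader, and the documents support none of them:
- *Phase I shows that Quadri is more reactogenic.* It rests on 6/29 v 1/28 with p = 0.102. Placebo lay above Plus, and all systemic reactions were rated mild.
- *Clinical efficacy is a listed goal that the plan ignores.* It is in the general objective and the secondary endpoints, not in the list of goals.
- *Influenza/ARI is only plotted.* Per-group incidence with a 95 % interval is also planned.
- *The plan will claim equal efficacy if the curves look alike.* Nothing in the text says so.

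**Conclusion.** The gap is real and moderate. Safety and reactogenicity are to be compared with Grippol Plus, and influenza/ARI falls within a comparative objective, yet Section 8.1 specifies no between-group difference or interval for either. Phase I does not settle the question: 17.1 points, with an interval from just below zero to 35.1. This trial could narrow the uncertainty to about ±4 to 7 points for Group A against pooled B and C, given assumed rates of 5 to 20 %, and to about ±4 to 8 points against one trivalent group. Those widths rest on assumed rates and normal approximations. Applying the planned 5 % dropout changes the pooled figures by no more than 0.2 points. The primary analysis and sample size are not affected.

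**What to change.** **Section 8.1, Safety analysis.** Add, for any local reaction, any systemic reaction and any adverse event, the risk difference with a two-sided 95 % interval (Newcombe or Miettinen-Nurminen). Give it for Group A minus pooled B and C, and also for A minus B and A minus C, since each trivalent vaccine lacks one B lineage. State the denominator for systemic reactions: the smooth-course volunteers of Section 7.2, with all vaccinated volunteers as a check, because the smooth-course restriction depends on events after randomization.

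**Section 8.1, incidence of influenza and ARI.** Add the Day-180 difference in Kaplan-Meier cumulative incidence with a 95 % interval for the same three contrasts. State that an interval including zero does not show equal efficacy.

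Label all of these as unadjusted estimates, not tests.

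**Cost.** A few table rows and no extra data or volunteers. The downside is several unadjusted intervals, one of which may exclude zero by chance; the label is there to prevent over-reading.
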